3.7. Visit Windows

3.7.1. Definition of Study Day

Study day is the day relative to the date of the first dose of study drug. Study Day 1 will be defined as the day of first dose of study drug administration.

Study day will be calculated from the date of first dose of study drug administration and derived as follows:

- For postdose study days: Assessment Date – First Dose Date + 1
- For days prior to the first dose: Assessment Date – First Dose Date

The last dose date for an individual study drug will be the end date on study drug administration eCRF for the record where the “subject permanently discontinued” flag is ‘Yes’. The last dose date will be defined as the maximum of the last dose dates of individual study drugs in a treatment group.

If there are subjects for whom the date of last study drug is unknown due to the reason that the subject was lost to follow-up and not able to be contacted, the date of last dose will be estimated using the maximum of nonmissing study drug start or stop dates, visit dates and laboratory collection dates (posttreatment visits and unscheduled visits are not included).

3.7.2. Analysis Windows

Subject visits might not occur on protocol-specified days. Therefore, for the purpose of analysis, observations will be assigned to analysis windows.

In general, the baseline value will be the last nonmissing value on or prior to the first dose date of study drug.

HCV RNA, vital signs, and safety laboratory data collected up to the last dose date + 2 days are considered to be on-treatment data and HCV RNA, vital signs and safety laboratory data collected after the last dose date + 2 days are considered posttreatment data. The analysis windows for on-treatment HCV RNA, vital signs and safety laboratory data are provided in [Table 3-4](#).

Table 3-4. Analysis Windows for On-treatment HCV RNA, Vital Signs and Safety Laboratory Data

Nominal Visit	LDV/SOF FDC 12 Weeks			LDV/SOF FDC ± RBV 24 Weeks		
	Nominal Day	Lower Limit	Upper Limit	Nominal Day	Lower Limit	Upper Limit
Baseline	1	(none)	1	1	(none)	1
Week 1	7	2	11	7	2	11
Week 2	14	12	21	14	12	21
Week 4	28	22	42	28	22	42
Week 8	56	43	70	56	43	70
Week 12	84	71	≥ 85	84	71	98
Week 16	NA			112	99	126
Week 20				140	127	154
Week 24				168	155	≥ 169

Subjects who participated in the PK Lead-in Phase will immediately roll over into the Treatment Phase with no interruption of study drug administration until the appropriateness of the dose is confirmed by PK and safety data from the PK-Lead-in Phase. These subjects will start at the Week 2 visit of the Treatment Phase. Week 1 records for these subjects will be chosen from Day 10 in the PK Lead-in Phase.

HCV RNA, vital sign, and safety laboratory data collected after the last dose date + 2 days will be assigned to the posttreatment follow-up (FU) visits. Visit windows will be calculated from the last dose date (ie, FU Day = collection date minus the last dose date) as shown in [Table 3-5](#).

Table 3-5. Analysis Windows for Posttreatment HCV RNA, Body Weight, Height, Vital Sign and Safety Laboratory Data

Nominal FU ^a Visit	HCV RNA, Body weight and Height			Vital Signs and Safety Laboratory Data ^b		
	Nominal FU Day	Lower Limit	Upper Limit	Nominal FU Day	Lower Limit	Upper Limit
FU-4	28	21	69	28	3	30
FU-12	84	70	146	NA	NA	NA
FU-24	168	147	210	NA	NA	NA

a FU-x visit = posttreatment Week-x follow-up visit.

b Vital signs (blood pressure, pulse, respiratory rate, and temperature) and safety labs will only be summarized for the FU-4 visit (up to 30 days after last dose).

3.7.3. Selection of Data in the Event of Multiple Records in an Analysis Window

Depending on the statistical analysis method, single values may be required for each analysis window. For example, change from baseline by visit usually requires a single value, whereas a time-to-event analysis would not require 1 value per analysis window.

If multiple valid nonmissing numeric observations exist in an analysis window, records will be chosen based on the following rules if a single value is needed:

- For baseline, the last available record on or prior to the date of the first dose of study drug will be selected. If there are multiple records with the same time or no time recorded on the same day, average (arithmetic mean) will be used for the baseline value.
- For postbaseline visits:
 - The record closest to the nominal day for that visit will be selected except for HCV RNA posttreatment follow-up visits, for which the latest record in the analysis window will be selected.
 - If there are 2 records that are equidistant from the nominal day, the later record will be selected.
 - If there is more than 1 record on the selected day, the average will be taken, unless otherwise specified.

If multiple valid nonmissing categorical observations exist in a window, records will be selected as follows:

- For baseline, the last available record on or prior to the date of the first dose of study drug will be selected. If there are multiple records with the same time or no time recorded on the same day, the value with the lowest severity will be selected (eg, normal will be selected over abnormal).
- For postbaseline visits, follow the same rules described above for postbaseline numeric observations, except that if there are multiple records on the same day, the most conservative value will be selected (eg, abnormal will be selected over normal).

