Australia	12 Weeks of treatment with LDV/SOF FDC	12 Weeks of treatment with LDV/SOF FDC	24 Weeks of treatment with LDV/SOF FDC	N/A	12 Weeks of treatment with LDV/SOF FDC	12 Weeks of treatment with LDV/SOF FDC	12 Weeks of treatment with LDV/SOF FDC
New Zealand	12 Weeks of treatment with LDV/SOF FDC	12 Weeks of treatment with LDV/SOF FDC	24 Weeks of treatment with LDV/SOF FDC	N/A	12 Weeks of treatment with LDV/SOF FDC	12 Weeks of treatment with LDV/SOF FDC	12 Weeks of treatment with LDV/SOF FDC
United Kingdom	12 Weeks of treatment with LDV/SOF FDC	12 Weeks of treatment with LDV/SOF FDC	24 Weeks of treatment with LDV/SOF FDC	24 Weeks of treatment with LDV/SOF FDC + RBV	12 Weeks of treatment with LDV/SOF FDC	12 Weeks of treatment with LDV/SOF FDC	24 Weeks of treatment with LDV/SOF FDC

TN = Treatment Naïve, TE = Treatment Experienced, N/A = Not Applicable

Subjects with GT -1, -3, and -4 were enrolled initially. GT-5 and GT-6 subjects will be included in those groups/cohorts actively enrolling subjects given confirmation of benefit:risk in adult patients has been obtained. If emerging LDV/SOF FDC data in GT-2 support treatment in adults, pediatric subjects with GT-2 will be subsequently enrolled.

The study will enroll both treatment naïve and treatment experienced pediatric subjects with up to 40 subjects allowed to be treatment experienced. Approximately 220 subjects, including subjects from the PK Lead-in Phase, will be enrolled in the Treatment Phase as follows:

- Group 1: Approximately 100 adolescent subjects (12 to < 18 years of age)
- Group 2: Approximately 120 pediatric subjects (3 to < 12 years of age)

The following definitions will be used for treatment experienced subjects:

- Interferon intolerant: Subject who discontinued therapy (≤ 12 weeks total) due to ≥ 1 adverse event
- Interferon non-responder: Subject who did not achieve undetectable HCV RNA levels while on treatment
- Relapse/breakthrough: Subject who achieved undetectable HCV RNA during treatment or within 4 weeks of the end of treatment but did not achieve a sustained virologic response (SVR)

All subjects who do not attain SVR or have viral relapse will be encouraged to discuss treatment with SOC therapy with their healthcare provider.

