5.6. Prior and Concomitant Medications

Concomitant medications taken within 30 days prior to screening, up to and including 30 days after the last dose of study drug, need to be recorded in the source documents and electronic case report form(s) (eCRFs).

The following medications are prohibited during the screening period and for a minimum of 28 days prior to the Day 1 visit through the end of treatment:

- Hematologic stimulating agents (e.g., erythropoiesis-stimulating agents (ESAs); granulocyte colony stimulating factor (G-CSF); thrombopoietin (TPO) mimetics)
- Chronic use of systemic immunosuppressants including, but not limited to, corticosteroids (prednisone equivalent of > 10 mg/day for > 2 weeks), azathioprine, or monoclonal antibodies (e.g., infliximab)
- Investigational agents or devices for any indication
- Drugs disallowed per prescribing information of REBETOL[®] for GT-3 subjects only

Concomitant use of certain medications or herbal/natural supplements (inhibitors or inducers of drug transporters i.e., P-gp) with study drug(s) may result in PK interactions resulting in increases or decreases in exposure of study drug(s). **Examples of representative medications which are prohibited from 21 days prior to Day 1 through the end of treatment are listed below (Table 5-1). In addition, the use of amiodarone is prohibited from 60 days prior to Baseline/Day 1 through the end of treatment.**

Table 5-1. Disallowed and Concomitant Medications to be Used with Caution

Drug Class	Agents Disallowed	Use with Caution
Acid Reducing Agents ^a		Proton- Pump Inhibitors, H2-Receptor Antagonists, Antacids
Anticonvulsants ^c	Phenobarbital, Phenytoin, Carbamazepine, Oxcarbazepine	
Antimycobacterials ^c	Rifabutin, Rifapentine, Rifampin	
Cardiac Medications	Amiodarone ^e	Digoxin ^b , Dabigatran ^b
Herbal/Natural Supplements ^c	St. John's Wort, Echinacea, Milk thistle (i.e., silymarin), Chinese herb sho-saiko-to (or Xiao-Shai-Hu-Tang)	
HMG-CoA Reductase Inhibitors ^d	Rosuvastatin	Atorvastatin, Simvastatin, Pravastatin, Pitavastatin, Fluvastatin, Lovastatin

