6.5. Post-Treatment Assessments

6.5.1. 4-Week Post-Treatment Visit (\pm 5 days)

- Vital signs, including body weight and height measurements
- Perform symptom-directed physical examination
- Assessment of AEs and concomitant medications
- Obtain blood samples for:
 - Hematology
 - Chemistry
 - HCV RNA
 - Viral sequencing (archive)
 - HBV DNA testing for subjects HBcAb positive at Screening

- Obtain urine sample for:
 - β -hCG pregnancy test for females of childbearing potential only
- Pregnancy prevention counseling including partner pregnancy prevention for male participants (all subjects \geq 12 years of age and subjects $<$ 12 years of age at the discretion of the Investigator based on subject's pubertal status)

Female subjects of childbearing potential on treatment with LDV/SOF FDC + RBV should be provided with Urine Pregnancy Test-Kits, instructed on their use, and requested to continue to self-monitor for pregnancy for 6-months after their last dose of RBV. If required by local regulations, additional pregnancy tests beyond 6 months may be added. The subject should be contacted every 4 weeks and asked to report results of the urine pregnancy tests. If a positive urine pregnancy test is reported, the subject should return to the clinic for a serum pregnancy test.

6.5.2. 12-Week Post-Treatment Visit (\pm 5 days)

- Vital signs, including body weight and height measurements
- Perform symptom-directed physical examination
- Assessment of SAEs
- Perform Tanner Pubertal Stage assessment
- Obtain blood samples for
 - Hematology
 - Chemistry
 - HCV RNA
 - Viral sequencing (archive)
 - HBV DNA testing for subjects HBcAb positive at Screening
- GT-3 subjects only: Obtain urine sample for β -hCG pregnancy test for females of childbearing potential only
- GT-3 subjects only: Pregnancy prevention counseling including partner pregnancy prevention for male participants (all subjects \geq 12 years of age and subjects $<$ 12 years of age at the discretion of the Investigator based on subject's pubertal status)
- Subject completes quality of life survey: Subject is to review questionnaire with a parent/guardian and write/mark answers directly onto the questionnaire

6.5.3. 24-Week Post-Treatment Visit (\pm 5 days)

- Vital signs, including body weight and height measurements
- Perform symptom-directed physical examination
- Assessment of SAEs
- Tanner Pubertal Stage Assessment
- A single X-ray of the left wrist, hand, and fingers for Bone Age Assessment

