6. EFFICACY ANALYSES

6.1. Key Efficacy Endpoint

6.1.1. Definition of the Key Efficacy Endpoint

The key efficacy endpoint is SVR12 defined as HCV RNA < LLOQ (ie, < 15 IU/mL) 12 weeks after discontinuation of all study drugs in the FAS. The COBAS[®] AmpliPrep/COBAS[®] TaqMan[®] HCV Test, v2.0 for use with the High Pure System will be used to measure HCV RNA.

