6.2. Secondary Efficacy Endpoints

6.2.1. Definition of Secondary Efficacy Endpoints

Secondary efficacy endpoints include the following:

- The percentage of subjects who attain SVR at 4 and 24 weeks after stopping therapy, defined as HCV RNA < LLOQ (ie, < 15 IU/mL) 4 and 24 weeks after stopping treatment (SVR 4 and SVR 24)
- The percentage of subjects with HCV RNA below LLOQ by study visit
- HCV RNA (\log_{10} IU/mL) and change from baseline in HCV RNA (\log_{10} IU/mL) through end of treatment (EOT)
- The percentage of subjects with virologic failure as the following:

On-treatment virologic failure

- HCV RNA \geq LLOQ after having previously had HCV RNA $<$ LLOQ, while on treatment, confirmed with 2 consecutive values (note, second confirmation value can be posttreatment), or last available on-treatment measurement with no subsequent follow-up values (ie, breakthrough)
- $> 1 \log_{10}$ IU/mL increase in HCV RNA from nadir while on treatment, confirmed with 2 consecutive values (note, second confirmation value can be posttreatment), or last available on-treatment measurement with no subsequent follow-up values (ie, rebound)
- HCV RNA persistently \geq LLOQ through 8 weeks of treatment (ie, nonresponse)

Relapse

- HCV RNA \geq LLOQ during the posttreatment period having achieved HCV RNA $<$ LLOQ at end of treatment, confirmed with 2 consecutive values or last available posttreatment measurement
- The proportion of subjects with ALT normalization (defined as ALT $>$ ULN at baseline and ALT \leq ULN at each visit), presented by study visit.
- Characterization of HCV drug resistance substitutions at baseline, during, and after therapy with LDV/SOF

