6.2.2. Analysis Methods for Secondary Efficacy Endpoints

For analyses of HCV RNA $<$ LLOQ by visit while on treatment and during the posttreatment (SVR) follow-up period, subjects will be assigned a value at each visit based on the analysis visit windows specified in Section 3.7.2. Missing values will be imputed based on the categorical imputation rules described in Section 3.5.1. The 2-sided 95% exact confidence interval based on Clopper-Pearson method will be provided for the percentage of subjects with HCV RNA $<$ LLOQ at each visit in each treatment group. The overall category for “HCV RNA $<$ LLOQ” will be split into the following 2 subcategories: “ $<$ LLOQ TND” for subjects with target not detected and “ $<$ LLOQ detected” for subjects with $<$ LLOQ detected in tabular displays.

Graphs for the percentage of subjects with HCV RNA $<$ LLOQ over time during treatment will be displayed.

Summary statistics will be presented for absolute values and change from baseline in HCV RNA (\log_{10} IU/mL) by visit through EOT. Imputation rules described in Section 3.5.1 will be used to assign HCV RNA values for missing values at a visit that are bracketed by “ $<$ LLOQ TND” and/or “ $<$ LLOQ detected”. Otherwise, a missing = excluded analysis will be performed. Plots of the mean \pm SD and median (Q1, Q3) of absolute values and changes from baseline in HCV RNA through EOT will be presented.

For the SVR12 endpoint analysis, a summary table of the number and percentage of subjects with SVR12, virologic failure (VF), and Other will be created. All subjects who achieve SVR12 will be categorized as SVR12. Virologic failure will be descriptively summarized as “on-treatment virologic failure” and relapse (which will be broken down by study drug completed yes/no). Subjects who do not achieve SVR12 and do not meet criteria for VF will be categorized as Other. The denominator for relapse will be the number of subjects who had HCV RNA < LLOQ on their last observed on-treatment HCV RNA measurement; otherwise, the denominator will be the number of subjects in the FAS. Additional summary table will be provided by treatment group defined in [Table 3-3](#) for 3 to < 6 years of age subjects.

A concordance table between SVR12 and SVR24 will be provided by treatment group and total in each age group. Subjects with both observed SVR12 and observed SVR24 data will be included for this analysis.

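### HCV RNA taken after a child starts non-study anti-HCV therapy is not excluded, so a re-treated failure can be scored as SVR12 or SVR24

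*SAP*

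**What the plan says.** - **Endpoint.** SAP 6.1.1 defines SVR12 as HCV RNA below LLOQ (15 IU/mL) "12 weeks after discontinuation of all study drugs in the FAS". It sets no condition on other anti-HCV drugs. SVR4 and SVR24 in SAP 6.2.1 are built the same way.
- **Precedence.** SAP 6.2.2: "All subjects who achieve SVR12 will be categorized as SVR12". Virologic failure is reported only for those who are left. Relapse (SAP 6.2.1) must be "confirmed with 2 consecutive values or last available posttreatment measurement", but meeting that definition does not remove SVR12 status.
- **Windows and record choice.** SAP Table 3-5 sets FU-12 at Days 70 to 146 after last dose and FU-24 at Days 147 to 210. For several post-treatment HCV RNA values in one window, SAP 3.7.3 gives a rule "for which the latest record in the analysis window will be selected".
- **Failure rules.** Protocol 9.2.2 and SAP 3.5.1 turn missing values into failures. SAP 3.5.1 also carries SVR12 success forward to SVR24 when no later HCV RNA is collected.
- **Re-treatment.** Protocol 3.1.2 says that subjects who miss SVR or relapse "will be encouraged to discuss treatment with SOC therapy with their healthcare provider". Protocol 3.3 leaves HCV RNA unblinded, and Protocol 3.5 keeps children who stop study drug early in post-treatment follow-up. Starting other anti-HCV therapy appears only as a bar to the separate long-term study (Protocol 3.8 and 6.5.3).
- **Medication recording.** Protocol 5.6 requires it "up to and including 30 days after the last dose of study drug". Protocol Appendix Table 3 schedules a medication review at post-treatment Week 4 only.

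**The concern.** The protocol expects that some children who fail will receive other therapy while they are still attending study visits. An HCV RNA below LLOQ measured on or after that therapy says nothing about LDV/SOF. It is an observed value, however, so no missing-data rule applies to it, and the endpoint definition accepts it.

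SVR12 is the key efficacy endpoint of a single-arm study, reported as a rate with an interval and no comparator. A misclassification of this kind can only move the rate upwards.

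**Working it through.** **1. The plan's own precision.** Inputs from SAP 1.3: n = 100 and n = 120, expected SVR12 of 90%. Half-width = 1.96 × √(0.9 × 0.1 / n).
- n = 100: 5.88 points (stated 5.9).
- n = 120: 5.37 points (stated 5.4).

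Both figures reproduce and are not in dispute. They give the scale for what follows.

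**2. Time available for re-treatment,** from the nominal days in SAP Table 3-5 (28, 84, 168):

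| Failure known at | Days to FU-12 | Days to FU-24 |
|---|---|---|
| End of study drug (on-treatment failure) | 84 | 168 |
| FU-4 relapse | 84 − 28 = 56 | 168 − 28 = 140 |
| FU-12 relapse | none | 168 − 84 = 84 |

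Confirmation and access to therapy use up part of each interval. SVR24 has more time in every row.

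**3. Cases traced through the rules.**
- *Relapse at FU-4, re-treated, below LLOQ at FU-12.* The FU-12 value is observed and meets SAP 6.1.1. SAP 6.2.2 then classes the child as SVR12, even if the relapse was confirmed. If no later sample is taken, SAP 3.5.1 makes the child an SVR24 success too.
- *Relapse at FU-12, re-treated, below LLOQ at FU-24.* SVR12 is correctly a failure, but SVR24 is scored as a success.
- *On-treatment failure, study drug stopped, re-treated.* The path is the same as in the first case, with 84 days to FU-12.

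In each case a single scheduled value is enough. The rule for choosing among several records is not needed for the error to occur.

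**4. Size.** One child adds 1/100 = 1.0 point in Group 1 or 1/120 = 0.83 point in Group 2. The documents give no re-treatment count, so k, the number wrongly counted as SVR12, is assumed to run from 0 to 5. The table shows the true rate behind a reported 90%, with Clopper-Pearson 95% CIs as in SAP 6.1.2:

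| k | Group 1 (n = 100) | Group 2 (n = 120) |
|---|---|---|
| 0 | 90.0% (82.4 to 95.1) | 90.0% (83.2 to 94.7) |
| 1 | 89.0% (81.2 to 94.4) | 89.2% (82.2 to 94.1) |
| 3 | 87.0% (78.8 to 92.9) | 87.5% (80.2 to 92.8) |
| 5 | 85.0% (76.5 to 91.4) | 85.8% (78.3 to 91.5) |

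SVR12 is also reported by treatment group. At most 40 children may be treatment-experienced, so one child in such a group is worth at least 1/40 = 2.5 points.

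**5. Can the cases be found?** The FU-4 visit falls on Day 28 ± 5, that is Day 23 to 33, and recording stops at Day 30. A relapse first seen at FU-4 leaves at most 30 − 23 = 7 days in which new therapy must be recorded. One first seen at FU-12 leaves none. Prompt re-treatment of an on-treatment failure would be recorded, but no SVR rule uses that record.

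**The case against.** The strongest reply is that few children, perhaps none, would be affected. Protocol 1.1 names peginterferon plus ribavirin, for 24 or 48 weeks, as the paediatric standard of care. It reports SVR24 of 36% to 53% in genotype 1 and notes that many paediatricians prefer to delay treatment. A child who relapses at FU-4 has about 8 weeks to be confirmed, start therapy and fall below 15 IU/mL. Some non-responders under the plan are failures only because data are missing, and without an observed value they cannot be misclassified. This stands as a limit on frequency, above all for SVR12. It does not close the gap: the child need only be below LLOQ when sampled, possibly still on the new drug, and SVR24 allows more time.

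Three stronger readings are tempting, and the documents do not support them.
- *The wide windows and the latest-record rule are at fault.* One HCV RNA draw is scheduled at each of FU-12 and FU-24, within ±5 days, so the rule matters only when extra samples exist. Without re-treatment it is conservative, because it picks up late relapse.
- *Re-treated children cannot be identified.* Therapy started within 30 days is recorded, and eligibility for long-term follow-up turns on other therapy. A value at or above LLOQ followed by one below it is visible in the data. For observed SVR12 failure with SVR24 success, the concordance table in SAP 6.2.2 shows the discordance. None of these reliably gives a start date, so identification is uncertain but not impossible.
- *The earlier a child fails, the more time there is.* Windows run from last dose, so stopping at Week 4 or Week 8 leaves the same 84 days to FU-12. The difference is only between on-treatment failures and post-treatment relapsers.

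**Conclusion.** The point holds as an omission. Followed as written, the plan scores a failed and re-treated child as SVR if the FU-12 or FU-24 value is below LLOQ. The direction is certain (upwards only) and the amount is not. It is 1.0 or 0.83 points per child, and up to 5.0 or 4.2 points for five children, against planned half-widths of 5.9 and 5.4. The range of 0 to 5 is an assumption, and zero is credible. SVR24 is more exposed than SVR12. No stated sample size or precision figure changes. The gap deserves correction because it touches the key endpoint and because the data needed to repair it afterwards may be incomplete.

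The blacked-out exploratory section (SAP 6.3) was not counted either way.

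**What to change.** 1. In SAP 3.5.1 and 6.1.1, state that HCV RNA on or after the start of any non-study anti-HCV therapy is not used. The subject is then a failure for SVR at that visit and all later ones. Say explicitly that SVR12 is not carried forward to SVR24 for such a subject; otherwise discarding the FU-24 value would trigger that imputation.
2. Keep the latest-record rule in SAP 3.7.3.
3. In Protocol 5.6 and Appendix Table 3, record the start date of any non-study anti-HCV therapy through post-treatment Week 24.

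**Cost.** The SAP wording is trivial and can be settled before the database is finalised. The recording item is a small CRF change, but it is also a protocol modification that needs ethics approval (Protocol 10.1.2 and 10.2.1). SAP Table 3-1 already reflects the subjects actually enrolled, so the item may come too late for children who have finished follow-up. For them, use recorded medications and long-term follow-up eligibility information, and query any child whose post-treatment HCV RNA goes from at or above LLOQ to below it. The reported SVR rates may come out slightly lower.
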